bleeding, sepsis, liver dysfunction, trauma).²⁸⁻³¹ In all the studies the administration of fibrinogen was well-tolerated. No severe adverse events attributable to fibrinogen concentrate were recorded.

Although the current literature shows that concentrated fibrinogen has a good safety profile the above authors have the opinion that there is a strong need for better studies because the evidence is restricted to case studies and retrospective analyses.

The expected outcome is that primary use of blood products (packed red cells, platelets, FFP, and Cryo) will be reduced. This overall reduction due to the use of fibrinogen concentrate will also reduce the side effects associated with the use of packed red cells, platelets, FFP, and Cryo and will significantly benefit patients.

Capital Health

ROUTE OF ADMINISTRATION, DOSAGE, DOSAGE REGIMEN, AND TREATMENT PERIOD

Fibrinogen dosing will be based on the results of the FIBTEM[®] analysis. The amount of fibrinogen concentrate corresponds to approximately 0.5 g of fibrinogen concentrate needed to raise MCF by 1 mm in a 70 kg patient.^{9,10,26} The maximum amount of fibrinogen concentrate used in this study will be 10 g in any participant. In the placebo group, the standard hemostatic algorithm involving the use of plasma, Cryo and platelets (Figure 1), will be used as per the standard of care currently in place at CDHA.

Once randomized to treatment, the test compound will be administered through the central line (usually internal jugular vein catheter) by the anesthesiologist within 10 minutes (25-50 ml/minute). Since high doses of anticoagulants are used in this surgical population while on cardiopulmonary bypass it is important that the test compound is administered in a relatively short period of time to boost the fibrinogen level.

The trial will be conducted in compliance with the protocol, GCP and the applicable regulatory requirements.

STUDY POPULATION

All patients will be recruited from the Queen Elizabeth II Health Sciences Center (QEIIHSC), Halifax, Nova Scotia, which is the sole tertiary cardiac surgery referral center in Nova Scotia. There are approximately 1000 open heart surgical procedures performed yearly, including more than 700 isolated CABG procedures.

REFERENCES

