Primary outcome: Cumulative perioperative amount (number of units and total volume) of blood components used between the start of surgery and 24 hours after administration of the study drug or placebo. 'Blood Components' are defined as all fresh components of blood (RBCs, plasma, platelets, and Cryo).

Secondary outcomes: To determine the effect of RiaSTAP™ on fibrinogen levels, hematocrit, PT, PTT, INR, platelet count, Hemoglobin (Hb), Thromboelastometry (ROTEM®, CT, CFT, Angle, MCF), CVICU-stay, Hospital-stay, In-Hospital Mortality, Hemoglobin, adverse events (anaphylaxis, stroke, myocardial infarction, pulmonary embolism, and deep vein thromboembolism) and usage of factor VII concentrate and human prothrombin complex (factors II, VII, IX, X), total avoidance of transfusion after CPB (24h after administration of study drug or placebo).

METHODOLOGY

The proposed trial will be a prospective, single-centre, double blind, randomized, controlled trial comparing blood product utilization between patients receiving saline therapy (PLACEBO) compared to fibrinogen therapy (FIB) in the setting of perioperative ~~surgical bleeding~~ **blood management in patients with low or low normal fibrinogen levels** after complex cardiac surgery. Blood products refer to any manufactured product derived from blood or plasma (albumin, fibrinogen, rFVIIa, human prothrombin complex, etc.).

Intervention

Prospective, randomized controlled study involving two groups: fibrinogen group (FIB) and saline group (PLACEBO), with a standardized anaesthesia protocol. Anesthesia management, surgical technique, post-operative management and follow-up will be as per the standard of care for this surgical population.

In-Hospital Follow-up: All postoperative cardiac surgery patients will be followed for the duration of their hospital stay. Blood work and amount of blood components and products will be assessed at the end of surgery, 12hr, and 24hr after delivery of the study medication. The study endpoint for the primary outcome parameter (amount of blood components) will be 24h after administration of the study medication.

Other outcomes assessed include Thromboelastometry (ROTEM®, EXTEM, INTEM, HEPTM, FIBTEM, CT, CFT, Angle, MCF), CVICU-stay, Hospital-stay, In-Hospital Mortality, Hemoglobin, and adverse events.

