The Blood Transfusion Services are able to unblind for the clinical treatment of a patient. Please refer to the site Standard operating procedure for more details of this process. If a patient's treatment is unblinded before the 24 hour primary end point their data will not be used in the analysis.

STATISTICS

Sample size

The primary outcome of interest will be overall need for blood transfusion at 24hr after surgery (including all used blood components from the start of surgery). For the sample size calculations G*Power version 3.1.2 was used.

Based on the available literature ^{9,10,12}, the investigator hypothesized a 70-90% reduction in total units of blood products in the group receiving fibrinogen compared with the group receiving conventional therapy. An estimate of blood product requirement in the group receiving conventional therapy is mean 3.4 units (standard deviation 5.9) based on our data from 2005 to 2007 for AVR+CABG, MVR+CABG, AVR+MVR, and Aortic root repair +/-AVR. Standard deviation 5.9 was used for both groups. Blood product requirement in the two groups will be compared using the Mann-Whitney U test for two independent samples. The sample size calculation was based on a two-tailed test with $\alpha = 0.05$, for $\beta = 0.2, 0.1, \text{ and } 0.05$. The sample sizes shown Table 1 represent the number of patients required in each group.

Details of the planned analysis

~~Individual case forms will be completed by the research coordinator for individual patients.~~ **The research coordinator will complete individual case forms for individual patients.** These forms will be detailing demographic characteristics,

Capital Health

intra-operative, post-operative and follow-up outcomes. Outcome data and blood samples will be collected according a lab/data schedule (Table 2). ~~All data will be reviewed by the appropriate clinical outcomes committee.~~ **The Sponsor will review all data.** Once reviewed all data will entered and maintained electronically.

Primary outcome: Blood component requirement in the two groups will be compared using the Mann-Whitney U test for two independent samples.

Secondary outcomes: Univariate comparisons between patients randomized to FIB and patients randomized to PLACEBO group will be carried out based on pre-, intra-, and post-operative variables using Chi-square tests for dichotomous variables, two-tailed t-tests for continuous variables and Wilcoxon rank sum tests for nominal variables.

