Approximately 200 complex cardiac procedures are performed annually in Halifax by nine cardiac surgeons. Of these patients, conflicting studies and patients being disqualified on the basis of exclusion criteria will result in a maximal annual number of eligible patients of 100 per year. We would plan to recruit 222 patients for this study. With a length of follow up of 6 months and using administrative data of an already well established data base we are expecting a rate of loss under 5%.

DATA HANDLING AND RECORD KEEPING

Data will be collected from patient charts and health records, the anesthetic record as well as the Maritime heart center cardiac surgery database. A data collection sheet will be filled out by the study nurse for patients included in the study. Follow-up data will be collected from patients themselves. In cases where patients have adverse outcomes, this information will be obtained from hospital records and the patient.

A data collection form will be used to collect study information and will be completed by the designated study personnel for participants. These forms will be detailing demographic characteristics, intra-operative, postoperative and follow-up outcomes. Individual data forms will record: the perioperative amount of blood products used (packed red cells, FFP, platelets,

Capital Health

Cryo). Also fibrinogen levels, hematocrit, PTT, INR, platelet count, Hemoglobin, Thromboelastometry (ROTEM®, CT, CFT, Angle, MCF), CVICU-stay, Hospital-stay, In-Hospital Mortality, Hemoglobin, adverse events (anaphylaxis, stroke, myocardial infarction, pulmonary embolism, and deep vein thromboembolism) and usage of factor VII concentrate and human prothrombin complex will be collected for study purposes. All data will be reviewed by the appropriate **outcome** committee. Once reviewed all data will be entered and maintained electronically on a designated CDHA computer.

Data will also be collected using the Maritime Heart Center (MHC) cardiac surgery database. This database is a prospectively collected, clinical database that captures detailed information on a wide range of pre-operative, intra-operative, and in-hospital postoperative variables including post-operative complications and in-hospital mortality for all patients undergoing cardiac surgery at the QE II Health Sciences Center.

QUALITY CONTROL AND QUALITY ASSURANCE PROCEDURES

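### Thromboembolic safety events are listed one by one and given only a chi-square test, with no combined outcome, effect estimate or interval, in a trial sized on units transfused

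*Combined protocol and SAP*

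**What the plan says.** The Primary and secondary outcomes section (under Trial Design) names the safety events as "adverse events (anaphylaxis, stroke, myocardial infarction, pulmonary embolism, and deep vein thromboembolism", and the secondary objective gives the same list. Assessment of Safety lists them again among the adverse events, captured from randomization to six months. Table 2 gives each its own entry at discharge.

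The method is in Details of the planned analysis (under Statistics): univariate comparisons between arms "using Chi-square tests for dichotomous variables, two-tailed t-tests for continuous variables and Wilcoxon rank sum tests for nominal variables". No composite, effect measure, interval or exact test appears there or elsewhere.

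On size, Estimated Recruitment Rate says "We would plan to recruit 222 patients for this study". The calculation behind it concerns blood product units only, with a control "mean 3.4 units (standard deviation 5.9) based on our data from 2005 to 2007". No safety event rate or safety power is given.

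On the state of knowledge, the Benefits section reports that earlier authors hold that "there is a strong need for better studies because the evidence is restricted to case studies and retrospective analyses".

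**The concern.** Thrombosis is a main harm that the protocol discusses for fibrinogen concentrate, and it describes the existing safety evidence as weak. A blinded, placebo-controlled comparison followed for six months would be better evidence than the case studies and retrospective series cited. If the events are analysed as listed, however, the output is a set of chi-square p-values on a handful of events each. Non-significance is then the expected result even if fibrinogen doubles the risk, and a bare p-value does not show how large an excess is still compatible with the data. At stake is the safety reading of a trial whose authors foresee first-line use if results are positive. The primary analysis is not affected.

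**Working it through.** **Inputs.** Total 222 (Estimated Recruitment Rate). Table 1 is per group ("The sample sizes shown Table 1 represent the number of patients required in each group"), so 222 = 2 × 111, taking 1:1 allocation as implied. Two-sided alpha is 0.05. Control-arm event rates are not in the documents. The range assumed here is 1% to 3% for a single event and 5% to 10% for a composite.

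**Step 1: the plan's own figure.** For 3.4 to 1.0 units with SD 5.9, n = 2(1.960 + 0.842)² × (5.9/2.4)² = 94.9, so 95 per group for a comparison of means. Dividing by 0.864, the minimum asymptotic relative efficiency of the Mann-Whitney test, gives 110. The noncentral-t version gives 111, as in Table 1. The trial is therefore sized on the primary outcome alone.

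**Step 2: power for single events.** With x₁ and x₂ events and n = 111 per arm, z = [(x₁ − x₂)/n] / √[p̄(1 − p̄) × 2/n], where p̄ = (x₁ + x₂)/(2n). Exact power is the summed binomial probability of all pairs with |z| > 1.96.

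| Control to active | Expected events per arm under the pooled rate | Exact power | Patients per arm for 80% power (normal approximation) |
|---|---|---|---|
| 1% to 2% | 111 × 1.5% = 1.7 | 6.5% | 2319 |
| 2% to 4% | 111 × 3% = 3.3 | 12% | 1141 |
| 3% to 6% | 111 × 4.5% = 5.0 | 17% | 749 |

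A doubling reaches 80% power only at a control rate of about 16%. The conclusion therefore does not depend on the exact rate assumed. Moreover, 111 is a ceiling: the expected loss of under 5% is not added to 222, and patients unblinded before 24 hours are left out of the analysis. At 105 per arm, power for 2% to 4% is 13% by the normal approximation, against 14% at 111.

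**Step 3: reliability of the p-value.** Take 4 v 0. Then p̄ = 4/222 = 0.0180 and z = 0.0360/√(0.0180 × 0.9820 × 2/111) = 2.02, so p = 0.044. Fisher's two-sided p = 2 × (111 × 110 × 109 × 108)/(222 × 221 × 220 × 219) = 0.12. The two methods fall on opposite sides of 0.05.

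**Step 4: what an interval would show.** For 3 v 3 events, the Wald half-width is 1.96 × √(2 × 0.0270 × 0.9730/111) = 4.3 percentage points; Newcombe's method gives 5.3. With no events in an arm, the two-sided 95% upper limit is 1 − 0.025^(1/111) = 3.3%. A non-significant p-value conveys neither.

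**Step 5: the composite.** By the same enumeration, power for a doubling is 30% (5% to 10%), 36% (6% to 12%), 46% (8% to 16%) and 56% (10% to 20%). If only half of an 8% composite doubles, the change is 8% to 12% and power is 17%. Six v 6 events gives a Newcombe interval of −6.6 to +6.6 points; 11 v 11 gives −8.2 to +8.2.

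**The case against.** Several objections have force.

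- **Separate testing is inferred.** The outcomes section gives one bracketed list under adverse events, and the analysis sentence is generic. A test of any listed event would also fit the words. This stands: the firm statement is that the plan does not say how the events are combined, and that the only method offered is a univariate chi-square.
- **The cause is sample size, not the missing composite.** A reader might infer that the comparison is uninformative because the events are not pooled. The figures do not support that. Rare events and 111 per arm are the cause, and a pooled outcome remains underpowered for a doubling. Its absolute interval is also wider than that for a single rare event.
- **The trial is not blind to all harm.** A reader might infer that the safety comparison can show almost nothing. That goes too far: an increase from 5% to 15% would be detected with 73% power.
- **No safety claim is made.** The hypothesis is superiority in bleeding management, and the first-line-use statements are tied to reduced transfusion. A prediction that the report will present null tests as proof of safety cannot be drawn from the documents.
- **Other safeguards exist.** The Data and Safety Monitoring Committee, which includes an independent statistician, reviews drug-related events, and there is an interim analysis at half enrolment. This is a real protection, but the review of individual events is not a published between-arm estimate with its uncertainty.

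None of these supplies the missing effect estimate, interval or exact method.

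**Conclusion.** The point holds as a worthwhile, low-cost improvement. It is not a defect in the primary analysis. The safety events are listed separately, the stated method is a univariate chi-square, and nothing planned tells the reader what excess risk is compatible with the result. Exact power for a doubling is 6.5% to 17% at assumed control rates of 1% to 3%. These figures rest on 111 analysed per arm and on assumed rates, but a doubling stays below 80% power at any control rate under about 16%. A composite raises power to about 36% to 46% for a doubling from 6% to 8%, provided fibrinogen doubles the pooled rate and not only some components. It would not establish safety, and the documents do not support reading it that way.

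**What to change.** Add to the analysis plan, before any unblinding:

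1. One composite safety outcome: any of stroke, myocardial infarction, pulmonary embolism or deep vein thrombosis from study drug to discharge, reported as a risk difference with a 95% confidence interval.
2. Each component and anaphylaxis as counts per arm with exact intervals. Where a p-value is given, use Fisher's exact test in place of chi-square.
3. A statement that non-significant results will not be read as evidence of safety.

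Add a six-month version only after the follow-up sources are reconciled. The continued Table 2 omits stroke and uses an undefined thrombosis item. After Discharge Follow-up does list stroke but has the same undefined item. Assessment of Safety names stroke, pulmonary embolism and deep vein thrombosis with capture to six months.

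**Cost.** The discharge version needs plan wording and one added analysis of events already recorded. The six-month version also needs event definitions and a corrected schedule. Downsides: the composite mixes events of different severity, so components must stand beside it, and it is diluted if only some components are affected. Fisher's test is also more conservative: at 2% to 4% its power is 5.4%, against 12% for chi-square. That is a further reason to rest the report on intervals.

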Any patients with evidence of study drug related adverse events at follow-up will be reviewed by the Data and Safety Monitoring Committee (DSMC) to review all the supporting evidence. The (DSMC) will consist of at least one anesthesiologist, one surgeon and a statistician not otherwise associated with the trial. Their role will be to review the available evidence provided by the research coordinator for the follow-up of all patients including in-hospital and follow-up study drug related adverse events. The outcomes of interest are listed above and will follow-strict study definitions as outlined. All outcomes will be based on consensus of the DSMC.

There will be an interim analysis performed by the Data and Safety Monitoring Committee. This analysis will be conducted when half of the patients have been enrolled. The final analysis will be conducted once all enrolled patients have reached their follow-up date. All final analysis will take into consideration that an interim analysis was conducted.

In case the study is terminated prematurely, the REB will be notified within 14 days in writing including the reason for the termination. If the termination is related to an emergent safety issue, the notification will be faxed to the REB office or preceded by a telephone call to the Chair or REB Coordinator. The study will be unblinded and all patients having received fibrinogen concentrate will be notified in writing and by direct contact via a telephone call of the study termination as well as

Capital Health

the reason for termination. Patients will also be informed of any emergent safety issues or adverse outcomes. Patients will be instructed on how to proceed in terms of medical care and follow up investigations.

RANDOMIZATION METHOD

Informed consent will be obtained from the patient prior to the operation either in the same-day surgery clinic or at the bedside if the patient has already been admitted to hospital pre-operatively. The randomization process will be performed with the help of software (G*Power version 3.1.2). Treatment allocation cards will be provided by the study Sponsor and placed in sealed, opaque envelopes for safe storage in a secure location to preserve the integrity of the blinding. The study drug designate will withdraw the envelope directing the patient's randomization to the FIB group or the PLACEBO group. Both the surgeon and anaesthesiologist will be blinded to patient randomization.

Randomization process

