As per the standard of care in this surgical population, all post-operative cardiac surgery patients will be taken immediately to a dedicated cardiovascular intensive care unit (CVICU). All patients will receive respiratory and hemodynamic support as needed. Each patient will be required to meet standard hospital criteria both prior to extubation and prior to transfer to the intermediate-care unit (IMCU). Discharged patients will be transferred to an intermediate-care unit or general-care ward under the care of the same cardiac surgical team. All patients will be monitored continuously for a minimum of 24 hours. In case of a post-operative bleeding in CVICU the same algorithm (Figure 3) like in the OR will be used. In case of surgical bleeding a re-sternotomy will be performed. Diffuse bleeding will be treated with blood components (step 2 -5, Figure 3). Patients having a valve replaced with a mechanical valve will receive heparin or warfarin 48 hours after surgery. All other patients will get ASA (acetylsalicylic acid, Aspirin®, Bayer Canada) on the first postoperative day (anticoagulation protocol, Division of Cardiac Surgery, QEII, Halifax, Canada).

ASSESSMENT OF SAFETY

Adverse Events

The following treatment-emergent and adverse effects will be captured during this study from the date ~~the consent was signed~~ of randomization to the 6 month follow-up:

Treatment-emergent adverse events

- Pleural effusion
- Atrial fibrillation
- Postoperative Delirium
- Reoperation because of surgical bleeding and unknown bleeding
- Air embolism

Adverse events (A/E) and Serious adverse events (SAE)

- Anaphylaxis
- Stroke
- Myocardial infarction
- Pulmonary embolism
- Deep vein thromboembolism
- Sternal wound infection
- Recurrent angina
- Angiography
- Percutaneous coronary intervention (PCT)
- Repeated cardiac surgery
- Cardiorespiratory arrest
- Cerebral hemorrhage
- Death

All serious unexpected adverse drug reactions will be reported to Health Canada as per ICH/GCP guidelines.

Unblinding

Unblinding for this study will occur when:

1. Clinical treatment decisions need to be made and when an unexpected serious adverse event occurs and the intervention must be made known.
2. At the request of the Data Safety Monitoring Committee.

Capital Health

3. After 110 participants have reached the primary endpoint for interim analysis.
4. At the conclusion of the study to determine the effect of the intervention.

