All statistical analyses will be performed at the QEII Health Sciences Center using SAS version 9.2 (Cary, North Carolina). Data validation will be an integral part of this protocol and will be carried out using already established clinical and administrative patient databases available through the Division of Cardiac Surgery at the QEIIHSC. This will ensure 100% follow-up of all patients and data accuracy. ~~All discrepancy will be investigated by the clinical outcomes committee.~~ **The Data and Safety Monitoring Committee will investigate all discrepancies.** The Maritime Heart Center (MHC) cardiac surgery database is a prospectively collected, clinical database that captures detailed information on a wide range of pre-operative, intra-operative, and in-hospital post-operative variables including post-operative complications and in-hospital mortality for all patients undergoing cardiac surgery at the QE II Health Sciences Center. It is audited on an annual basis to ensure reliability of data capture. The MHC cardiac surgery database will be linked to the Canadian Institute for Health Information (CIHI) Discharge Abstract Database and the Nova Scotia Vital Statistics database through the Population Health Research Unit (PHRU) at Dalhousie University. The CIHI Discharge Abstract Database is a national administrative database that contains extensive data on all admissions to hospital and enables us to track all

Capital Health

readmissions to hospital. The Nova Scotia Vital Statistics database collects information on all deaths occurring within the province of Nova Scotia and enables us to track all-cause mortality following discharge from hospital. The following data will be obtained from the MHC-PHRU data link after 6-months follow-up for all patients:

- i) Cardiac related mortality
- ii) Readmission to hospital for acute myocardial infarction (AMI), acute coronary syndrome (ACS), or congestive heart failure (CHF)
- iii) Re-intervention including CABG and/or PCI

Estimated Recruitment Rate

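### The DSMC performs the interim analysis and also decides outcomes by consensus, but the plan neither limits who is unblinded nor keeps the deciding members masked to the patient's arm

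*Combined protocol and SAP*

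**What the plan says.** The METHODOLOGY section (In-Hospital Follow-up) gives the DSMC two tasks. On outcomes: "The outcomes of interest are listed above and will follow-strict study definitions as outlined", and then "All outcomes will be based on consensus of the DSMC". On monitoring: "There will be an interim analysis performed by the Data and Safety Monitoring Committee", with the timing "This analysis will be conducted when half of the patients have been enrolled". On membership: "The (DSMC) will consist of at least one anesthesiologist, one surgeon and a statistician not otherwise associated with the trial".

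The Unblinding list under ASSESSMENT OF SAFETY includes, as item 2, "At the request of the Data Safety Monitoring Committee" and, as item 3, "After 110 participants have reached the primary endpoint for interim analysis". Neither item says who is unblinded, or whether they receive individual codes or grouped results.

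STATISTICS (Details of the planned analysis) adds a third task, repeated under QUALITY CONTROL AND QUALITY ASSURANCE PROCEDURES: "The Data and Safety Monitoring Committee will investigate all discrepancies".

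Two other statements bear on the same work. STATISTICS says that the sponsor reviews all data. DATA HANDLING AND RECORD KEEPING gives that review to an outcome committee whose members, blinding and relation to the DSMC are not described.

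The only people whom RANDOMIZATION METHOD names as blinded to allocation are the surgeon and the anaesthesiologist.

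**The concern.** A monitoring committee needs comparative data, and an adjudicator should not know the arm of the patient being judged. The two roles can sit in one committee only if access is divided, and no section divides it.

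Myocardial infarction, stroke, pulmonary embolism and deep vein thrombosis are named secondary outcomes, and the committee also reviews events as study-drug related. Deciding whether such an event occurred, and whether the drug caused it, takes judgement. More is left to judgement because the protocol refers to strict definitions but lists these events without defining them. A member who has seen results by arm, and who may also learn or guess a patient's arm, could judge similar events differently in the two groups. At stake is the credibility of the safety comparison in a trial described as double blind. Bias of this kind cannot be reliably removed afterwards.

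**Working it through.** **Roles side by side**

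| Task | Body named | Section |
|---|---|---|
| Interim analysis | DSMC | METHODOLOGY; Proposed frequency of analysis |
| Decision on outcomes | DSMC, by consensus | METHODOLOGY |
| Investigation of discrepancies | DSMC | STATISTICS; QUALITY CONTROL |
| Request for unblinding | DSMC | Unblinding, item 2 |
| Review of all data | Sponsor | STATISTICS |
| Review of all data | Outcome committee | DATA HANDLING |

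The Unblinding list makes the interim an unblinding event, and METHODOLOGY has the DSMC perform it. That members see comparative results is therefore an inference, but the direct one. Whether they see individual codes is not stated. No section masks the material on which members decide events. Table 2 schedules fibrinogen and FIBTEM after dosing, and these values may suggest the arm if they are in the file.

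**Number of patients exposed**

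Inputs: 111 per group (Table 1, 70% reduction, 80% power); 222 planned and at most 100 eligible a year (Estimated Recruitment Rate); interim after 110 (Unblinding, item 3); adverse events captured to 6 months (ASSESSMENT OF SAFETY).

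1. The plan's own figure: 2 × 111 = 222. The 111 reproduces. With a difference of 2.4 units, SD 5.9, two-sided alpha 0.05 and 80% power, the t-test needs 96 per group. Dividing by 0.864, the minimum asymptotic relative efficiency of the Mann-Whitney test, gives 96 / 0.864 = 111.1, and the direct calculation gives 111.
2. Enrolled after the interim: 222 − 110 = 112, and 112 / 222 = 50.5%. If the interim is taken at half enrolment, 222 / 2 = 111, or 50.0%.
3. Earlier patients still in follow-up at the maximum rate: 100 per year × 0.5 year = 50. Upper bound: (112 + 50) / 222 = 162 / 222 = 73%. This counts patients with any open follow-up, not events.
4. If enrolment is even and events are spread evenly over six months (assumption), those 50 have on average half their follow-up left: 50 × 0.5 = 25, and (112 + 25) / 222 = 137 / 222 = 62%. If events occur mainly in hospital and are judged promptly, or accrual is slower, the figure falls towards 50%.

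The firm figure is about 50%. The range above it, up to 73%, depends on accrual and on when events occur. The documents give no expected rates for these events and nothing on how far unmasked judgement would differ, so neither the size nor the direction of any bias can be derived from them.

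**The case against.** - *A DSMC has to see unblinded data.* This stands. The gap is that the members who decide events are not required to be masked to the individual patient.
- *The consensus sentence closes a paragraph on drug-related adverse events, so it may cover only those.* This is a fair reading, although the sentence itself sets no such limit. Under the narrow reading the point still covers the safety events.
- *Most outcomes leave little to adjudicate.* This stands for the primary unit count, laboratory and ROTEM values, lengths of stay and in-hospital death.
- *The committee only investigates discrepancies, as part of validation against databases.* This stands. The text does not show that the DSMC would alter unit counts.
- *Linked databases supply cardiac mortality, readmission and re-intervention, and the cardiac surgery database is audited yearly.* This is a partial check. The protocol does not say how it relates to the committee's consensus, and drug-relatedness is not among the linked items.
- *Another body may review outcomes.* The sponsor and the outcome committee are both named, but neither is described as a blinded adjudicator. This adds a contradiction and does not supply a safeguard.

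A reader might infer that the adjudicators will know each patient's allocation after the interim. The documents do not support that: the Unblinding section does not say who receives codes, and grouped results do not reveal a later patient's arm. A reader might also infer that the primary result is compromised. A count of units to 24 hours gives little room for that.

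**Conclusion.** The point holds as a gap in stated access, confined to judged safety outcomes. One committee performs the comparative interim, decides outcomes and investigates discrepancies, with no rule on who is unblinded and no masking of the members who decide. About half the patients (112 of 222) would have all such events judged after the interim, together with later events in some of the earlier patients (at most about 50, at the maximum accrual rate). This rests on three assumptions: that the DSMC sees results by arm because it performs the analysis, that the trial continues to 222, and that the consensus sentence covers at least the adverse events. The change is worth making before the interim because it is cheap and the bias could not be undone later.

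**What to change.** 1. In METHODOLOGY and in the Unblinding list (items 2 and 3), state that allocation codes, whether for the interim or at the DSMC's request, go only to the DSMC statistician, except where a patient-safety decision needs an individual code.
2. State that the clinician members adjudicate each event from a packet with allocation and post-dose fibrinogen and FIBTEM results removed. The statistician, who holds the codes, takes no part in that consensus.
3. Require events already reported to be adjudicated before those members see interim results. Events that arise later are covered by the masked packets.
4. Move the handling of data discrepancies to blinded study staff.
5. Reconcile METHODOLOGY, STATISTICS, DATA HANDLING and QUALITY CONTROL so that one body is named for outcome decisions and one for data review.

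Labelling the arms A and B should not be relied on as the safeguard. Members would still see results by arm, and a large difference in fibrinogen or transfusion could identify them.

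The cost is protocol and charter wording and the small work of preparing masked packets. The existing membership allows the split, safety oversight is kept, and sample size and visit schedule do not change.
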